#### 4.3. TMS data analysis:

Peak to peak MEP amplitudes will be measured off-line. Recordings with EMG background activity will be excluded from further analysis. Data analysis SICE, SRC, rIHI, aIHI, and mapping: Peak to peak MEP amplitudes will be measured off-line. Recordings with EMG background activity will be excluded from further analysis. For

the SRC, the mean MEP amplitudes at each stimulus intensity will be calculated. For SICE, rIHI and aIHI, mean MEP amplitudes elicited at different ISIs and CS intensities will be calculated as a percentage of the mean test MEP amplitude evoked by TS alone. CS intensities will be expressed as percentage of the subject's MT. For mapping, the area will be calculated as the number of stimulation sites that produce an MEP in of the trials. The center of gravity (CoG), an estimate of the center of the map, will be calculated for each target muscle (ECU or FCU) based on the weighted MEP amplitudes at each active location. Statistical analysis: We will use linear mixed models to quantify the effects of subject type (cortical stroke patient, subcortical stroke patient, healthy control) along with other, measure-specific factors (outlined below) on outcomes of interest. The analyses will incorporate models of within-subject correlations stemming from multiple measures on each subject. Hypothesis testing will be conducted on mean model parameters at a significance level  $\alpha = 0.05$ . Post-hoc analysis will be corrected for multiple comparisons. For SICE: A mixed model will assess the effect of subject type and stimulated hemisphere (ipsi- or contralesional for the stroke subjects, zero for the controls) along with repeated measure CS intensity (60%, 80% MT) on relative conditioned MEP amplitude. For rIHI: A mixed model will be used to determine the dependence of relative conditioned MEP amplitude on subject type along with the repeated measures inhibition (cl\_M1 on il\_M1 and il\_M1 on cl\_M1) and ISI (2ms, 10ms). For aIHI: We will perform a mixed model analysis to determine the dependence of relative conditioned MEP amplitude on subject type along with the repeated measures inhibition (as above), time after go signal (0ms, 300ms, 400ms, and 450ms), and target size (small, extra-large). For SRC: The effect of the repeated measure stimulus intensity on the average MEP

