#### **4.4. Studies pertaining to Specific Aim #2: *Determine the role of contralesional M1 in motor performance during the post stroke recovery process***

In two studies (Study 1 and 2) we will test the effect of contralesional M1 transcranial magnetic stimulation on the subject's performance in a manual pointing task (4 different level of complexity, Presentation®) using either the paretic or the non-paretic hand in a counterbalanced randomized order and measures of motor excitability (IHI, SICI, MT, SRC, see above for details). To accomplish the goal of each study, a total of 6 experiments will be conducted in a randomized counterbalanced order. In Study 3 we will implement prediction and classification models to determine the predictive roles of variables measured in specific aim 1 on the supportive/detrimental role of cl\_M1 derived

from the effect of M1 downregulation by rTMS (Specific aim 2, study#1).

Study #1: Role of cl\_M1 on motor performance. In all subjects, we will test the effect of 1 Hz rTMS and sham cl\_M1 stimulation on the subject's performance in a pointing task of increasing difficulty using either the paretic or the non-paretic hand in a counterbalanced randomized order. Specifically, as previously described by our group in detail (Butefisch et al. 2003; Butefisch et al. 2008) rTMS at 90% MT will be used to decrease cl\_M1 function using a rapid Magstim (Magstim Company, UK). Briefly, coil position will be monitored online using Brainsight. EMG activity will be recorded from the ECU and other control muscles with the settings already detailed in Specific Aim 1. After determining the MT in the ECU hot spot (Rossini et al. 1994b), rTMS will be applied through the air-cooled figure-of-eight coil at 90% MT and 1 Hz frequency for 15 min (Butefisch et al. 2009). The effects will be compared to Sham stimulation applied at similar intensity and frequency (Butefisch et al. 2009). An additional two visits will be conducted for healthy subjects that include a repeat of the study measures described in specific aim 1 but we will stimulate at 80% rTMS to explore the effects compared to 90% rTMS and these visits will take the standard amount of time of 2-3 hours per visit. Preliminary data demonstrated different effects of different intensities and this needs to be confirmed in this population.

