Study #2: Effect of transient disruption of cl\_M1 on M1 excitability and IHI. In all subjects, we will test the effect of cl\_M1 stimulation on the outcomes of MT, SRC, SICE and IHI in both motor cortices one month post stroke. All measurement will be repeated 6

months after infarction. The data will be compared to the results of healthy age matched controls to establish abnormality.

*Statistical analysis:* The statistical tests performed in this section will mirror those in the specific aim 1 with the addition of repeated measures factors specifying acquisition time (pre- or post-rTMS stimulation) and time post-stroke (1 and 6 months). The mixed-models will investigate the effect of cl\_M1 stimulation on TMS outcomes MT, SRC, SICE, rHI over time post-stroke. Additionally, we will use the mixed model to assess the effects of cl\_M1 excitability (SICE from SA #1) and cl\_M1 activation (number of activated voxels and % signal change within ROI) on rTMS-related changes in TMS measures.

Study #3: Identify biomarkers in the subacute and chronic phase of stroke that predict either the supportive or detrimental role of contralesional M1 as determined by responses to specific intervention protocols. In this study, we will implement prediction and classification models to determine the predictive roles of variables in SA #1 on the supportive/detrimental role of cl\_M1 derived from the effect of M1 downregulation by rTMS (SA#2, study#1). Specifically, we will train (and test) a binary classifier to predict subjects' responses (positive or negative) to rTMS (down regulation and sham) at 1 and 6 months post-stroke based on sets of predictors defined by SAs # 1 & 2. The association between the set of predictors and the binary response will be established during an iterative cross-validation process involving training and testing, in which different data are used to establish a predictive model and to evaluate its performance. We will assess performance using standard measures of prediction accuracy such as sensitivity,

specificity, positive predictive value, and negative predictive value. We will employ and compare multiple modeling techniques such as the Elastic Net, logistic classifier, and Bayes classifiers. Developing and optimizing the classifiers will identify subsets of measures that have the greatest predictive power for forecasting the role of cl\_M1.

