## **6. Statistical analysis**

The statistical analysis of the data is outlined in each section of the study plan.

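### The 1 Hz versus sham comparison of pointing-task performance has no written model, and the stated reading of a response runs against the disruption logic that Study #3 depends on

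*Combined protocol and SAP*

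**What the plan says.** In Section 4.4, Study #1 sets up the comparison: "In all subjects, we will test the effect of 1 Hz rTMS and sham" stimulation of contralesional M1 on a pointing task of increasing difficulty, with either hand. It adds: "The effects will be compared to Sham stimulation applied at similar intensity and frequency". Healthy subjects have two further visits, at which "we will stimulate at 80% rTMS to explore the effects compared to 90% rTMS".

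The statistical paragraph for Aim 2 comes after Study #2. It says the tests mirror those of Aim 1 "with the addition of repeated measures factors specifying acquisition time (pre- or post-rTMS stimulation) and time post-stroke (1 and 6 months". It describes the models as examining the effect of contralesional M1 "stimulation on TMS outcomes MT, SRC, SICE, rHI over time post-stroke", plus a further model for rTMS-related changes in TMS measures. The Aim 1 models that it mirrors are in Section 4.3: "We will use linear mixed models to quantify the effects of subject type (cortical stroke patient, subcortical stroke patient, healthy control", with measure-specific factors.

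Study #3 trains a classifier for "responses (positive or negative) to rTMS (down regulation and sham) at 1 and 6 months post-stroke", with the supportive or detrimental role derived from Study #1. Section 6 adds no model: "The statistical analysis of the data is outlined in each section of the study plan".

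On interpretation, Section 2 says rTMS will temporarily interfere with the non-affected motor cortex. The next sentence takes improved performance as a sign of a supportive role and worse performance as a sign of a detrimental one. The Aim 2 hypothesis in Section 3 is that this cortex contributes to better performance of the paretic hand in patients with larger M1 and/or CST damage.

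**The concern.** Aim 2 asks what contralesional M1 does for motor performance. The comparison that answers this, 1 Hz against sham, is promised but not specified. The performance measure, the contrast, and the handling of hand and of the four complexity levels are all left open. The one paragraph that does specify Aim 2 models lists factors that leave sham out. A pre-to-post change alone cannot separate an rTMS effect from practice or fatigue within a session, and that separation is the purpose of the sham sessions.

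Study #3 then builds on the Study #1 response. It gives no rule for calling a response positive or negative. The only stated interpretation of a response is hard to square with stimulation meant to disrupt. If disrupting a region improves performance, the natural inference is that the region was hindering it. A classifier trained on reversed classes would point users to the wrong patients.

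**Working it through.** **1. Term check.** The table compares what Study #1 needs with what Sections 4.3, 4.4 and 6 write down.

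| Element | In a written model? |
|---|---|
| Pointing-task performance as outcome | No. Outcomes are MEP amplitude, MT, map area and centre of gravity in Aim 1, and MT, SRC, SICE, rHI and changes in TMS measures in Aim 2 |
| Stimulation condition (1 Hz, sham) | No |
| Hand (paretic, non-paretic) | No |
| Four-level task complexity | No. Target size is in the aIHI model, but the outcome there is conditioned MEP amplitude |
| 80% versus 90% intensity, healthy subjects | No |
| Acquisition time (pre, post) | Yes |
| Time post-stroke (1, 6 months) | Yes |
| Subject type | Yes, from Aim 1 |

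**2. What each contrast estimates.** Let τ be the rTMS effect and δ the within-session drift, with P for patients and C for controls.

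- Pre-to-post change after active rTMS: τ + δ.
- Group by acquisition time: (τ_P + δ_P) − (τ_C + δ_C). With shared drift this is τ_P − τ_C. Any rTMS effect common to both groups cancels along with the drift.
- Stimulation by acquisition time: (τ + δ) − δ = τ, if drift is the same in active and sham sessions.

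Only the third isolates the rTMS effect.

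**3. Size, hypothetical.** The documents give n = 30 healthy subjects (Section 5) and α = 0.05 (Section 4.3). I assume a two-sided test, drift in SDs of the change score, and 15 patients as an example, because no patient number is given. I use a one-sample t-test on change scores as a simplification of the mixed model. With τ = 0 the noncentrality is δ√n on n − 1 degrees of freedom.

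- n = 30: δ = 0.2 gives 0.2 × √30 = 1.10 and rejection 18.5%; δ = 0.3 gives 1.64 and 35.5%.
- n = 15: δ = 0.2 gives 0.77 and 11.2%; δ = 0.3 gives 1.16 and 19.2%.
- δ = 0: 5%, so there is no bias.

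The stimulation by acquisition-time contrast has noncentrality 0 in all these cases and stays at 5%.

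**4. Price of the sham contrast.** If the active and sham change scores have equal variance and correlation r, the ratio of standard errors is √(2(1 − r)).

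- r = 0: √2 = 1.41. r = 0.25: √1.5 = 1.22. r = 0.5: 1.00.
- Power for a true effect of 0.5 SD, n = 30, no drift: 75.4% uncontrolled, against 46.5%, 58.0% and 75.4% at those three values of r.
- Mean squared errors are equal when δ² + 1/n = 2(1 − r)/n, that is δ = √((1 − 2r)/n). At n = 30 this is √(1/30) = 0.18 SD at r = 0, √(0.5/30) = 0.13 SD at r = 0.25, and 0 at r = 0.5. Below these values the uncontrolled estimate is the more precise one.

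**5. Direction of response.** Section 2: disrupt, then improve, therefore supportive. Section 3: the cortex contributes to improved performance in patients with larger damage, so disrupting it in them should make performance worse. A patient who worsens under 1 Hz rTMS is therefore detrimental by Section 2 and supportive by the logic of Section 3. Study #3 derives its classes from down-regulation, so every label depends on which reading is used.

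**The case against.** The strongest reply is that the sham comparison is in the plan. Study #1 states it, and Study #3 mentions sham again. The model paragraph follows Study #2, names only TMS outcomes, and serves a comparison with healthy controls. This stands. A reader might infer that performance will be analysed pre-to-post with the sham data ignored. The documents do not support that: the performance model is unwritten, rather than written without sham. The rejection rates above therefore describe a literal use of the listed factors, not a stated intention for performance.

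It is also fair that drift, r and the patient number are assumed, and that sham control costs power when r is below 0.5. It is unclear whether sham sessions collect the excitability measures, since Study #2 does not name sham.

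A reader might also infer that one way of using sham in the Study #3 label is clearly best, such as subtracting the mean sham change rather than each patient's own. That cannot be settled here. Assume a sign-of-change label and equal true-effect and noise variances. The patient's own 1 Hz-minus-sham difference then has the wrong sign in 30.4% of cases if session noise is uncorrelated, but in 25.0% at a noise correlation of 0.5. A known mean sham change gives 25.0%. The ranking depends on a correlation that the documents do not give.

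On direction, the Abstract also mentions high-frequency rTMS, and improvement after facilitating stimulation could well mean support. But the sentence in Section 2 follows directly on disruption, and Study #3 uses down-regulation.

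**Conclusion.** The point holds as an omission plus an inconsistency. The main Aim 2 comparison, 1 Hz against sham on performance, has no specified model. The Aim 2 factor list that is written contains no stimulation term, so for the excitability outcomes, followed literally, it tests a change not controlled by sham. The group comparison cannot stand in for sham. This part rests on the text alone and on no assumed number.

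The interpretation in Section 2 is inconsistent with its own description of rTMS as disruptive and with the Section 3 hypothesis for patients with larger damage. Taken literally it reverses the Study #3 classes.

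The size of any bias is not derivable. It equals the within-session drift and is zero if there is none. The 18.5% and 35.5% figures are illustrations for assumed drifts of 0.2 and 0.3 SD at n = 30. This should be fixed before the data are analysed.

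**What to change.** 1. For pointing-task performance, name the outcome and state a mixed model with stimulation (1 Hz, sham) by acquisition time as the test of the rTMS effect. Include subject type, hand, complexity level and, in patients, time post-stroke.
2. Add the stimulation term to the excitability models wherever sham sessions collect those measures. Otherwise report those results as changes not controlled by sham.
3. Analyse the exploratory 80% versus 90% comparison separately, within healthy subjects. No patient has the 80% level, so crossing it with subject type would leave empty cells.
4. Reconcile Sections 2 and 3 on which direction of change under down-regulation means supportive. Then define the Study #3 positive/negative response on a sham-referenced change, with a cut-off fixed in advance.

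The cost is SAP wording and modest extra analysis for performance, because the sham sessions are already planned. The drawback is the precision loss in step 4 of the working when r is below 0.5. At r = 0.5 or above there is none.

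### Study 2 lets contralesional SICE explain its own pre-to-post change, without saying which recording supplies the predictor and with no sham term in the model

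*Combined protocol and SAP*

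**What the plan says.** The statistical paragraph of Study 2 (section 4.4) makes these statements:

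- **Predictor.** The mixed model will "assess the effects of cl\_M1 excitability (SICE from SA #1) and cl\_M1 activation", the latter measured by fMRI.
- **Outcome.** These effects are assessed "on rTMS-related changes in TMS measures". No measure is excluded, and the sentence before lists the measures: "The mixed-models will investigate the effect of cl\_M1 stimulation on TMS outcomes MT, SRC, SICE, rHI over time post-stroke". SICE is among them.
- **Hemispheres.** Study 2 covers "outcomes of MT, SRC, SICE and IHI in both motor cortices one month post stroke", so both contralesional (cl_M1) and ipsilesional (il_M1) SICE are outcomes.
- **Definition of change.** The Aim 1 models are extended by "repeated measures factors specifying acquisition time (pre- or post-rTMS stimulation) and time post-stroke (1 and 6 months". No other factor is added.
- **Sham.** Study 1, in the same section, says "The effects will be compared to Sham stimulation applied at similar intensity and frequency". The Study 2 model text does not carry this over.
- **Sessions.** For Studies 1 and 2, "a total of 6 experiments will be conducted in a randomized counterbalanced order". Nothing says which session supplies the Aim 1 SICE.

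Section 6 refers back to the individual sections for all statistics, so no safeguard is written elsewhere.

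**The concern.** SICE is a ratio of mean MEP amplitudes (section 4.3) and carries measurement error. If one recording serves both as the predictor and as the pre-rTMS value, its error enters the predictor with a plus sign and the change with a minus sign. Patients whose SICE happened to read high then appear to fall after rTMS, and those who read low appear to rise, even if rTMS does nothing. Averaging that recording with another dilutes the effect but does not remove it.

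This is the pattern a reader would expect if the response to stimulation depended on the excitability state of contralesional M1. Section 3 speaks of targeting contralesional M1 according to its state. A model without a sham term cannot tell the two explanations apart.

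**Working it through.** **Inputs.** Significance level 0.05 (section 4.3; sidedness not given, two-sided assumed). Section 5 gives 30 healthy subjects but no number of stroke patients, so n = 20, 30 and 40 are assumed. No reliability is given, so test-retest correlation r = 0.5, 0.7 and 0.9 is assumed. The plan states no power or error figure for this analysis, so there is none to reproduce.

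**Null model.** No rTMS effect and no state dependence: pre = T + e1, post = T + e2, with Var(T) = r, Var(e) = 1 − r and independent errors. Change = e2 − e1, with variance 2(1 − r). One change score per patient stands in for the planned mixed model.

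**A. Predictor is the pre-rTMS value.** Covariance with change is −(1 − r), so the correlation is −√((1 − r)/2): −0.50, −0.39 and −0.22 at r = 0.5, 0.7 and 0.9. At r = 0.7 and n = 30, Fisher's z gives atanh(0.387) × √27 = 0.4086 × 5.196 = 2.12, and Φ(2.12 − 1.96) ≈ 0.57. Simulation gives 0.58.

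**B. Predictor is the mean of the pre-rTMS value and one other recording.** Predictor variance is (1 + r)/2 and covariance with change is −(1 − r)/2, so the correlation is −½√((1 − r)/(1 + r)): −0.29, −0.21 and −0.11. At r = 0.7 and n = 30: atanh(0.210) × 5.196 = 1.11, and Φ(1.11 − 1.96) ≈ 0.20.

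**C. Predictor is a recording with independent error.** Covariance with change is 0, and the rate is 5%.

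Simulated false-positive rates (20,000 runs per cell):

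| n | A: r = 0.5 / 0.7 / 0.9 | B: r = 0.5 / 0.7 / 0.9 | C |
|---|---|---|---|
| 20 | 65 / 40 / 16% | 23 / 14 / 8% | 5% |
| 30 | 83 / 58 / 22% | 34 / 20 / 9% | 5% |
| 40 | 92 / 71 / 29% | 45 / 26 / 11% | 5% |

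**Does a sham contrast remove it?** Take the outcome as active change minus sham change, each session having its own pre value. Its variance is 4(1 − r).

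- *Predictor is the active session's own pre value.* Covariance is −(1 − r) and the correlation is −√(1 − r)/2, which is −0.27 at r = 0.7. With n = 30: atanh(0.274) × 5.196 = 1.46, and Φ(1.46 − 1.96) ≈ 0.31. Simulation at n = 30 gives 50%, 32% and 13% for r = 0.5, 0.7 and 0.9. The artefact remains.
- *Predictor is the mean of both pre values.* Covariance is −(1 − r)/2 + (1 − r)/2 = 0. Simulated rate 5%.
- *Predictor is independent of both sessions.* Covariance 0. Simulated rate 5%.

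**Scope.** The shared error links cl_M1 SICE only to the change in cl_M1 SICE. For an outcome whose errors are independent of SICE error, the simulated rate is about 5%.

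**The case against.** The strongest reply is that the premise is not established. The plan names the predictor as "excitability (SICE from SA #1") and treats the pre-rTMS acquisition as a level of a separate factor. With six experiments planned, a separate recording is at least as natural a reading, and then the rate is 5%. That stands: a reader might infer that the planned analysis must yield a false state-dependent effect, and the documents do not support this. They do not exclude it either. The Study 2 tests are said to follow the Aim 1 models with a pre/post factor added, which allows the pre-rTMS SICE to serve as the Aim 1 value.

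A second reply is that the reach is narrow. This also stands. A reader might infer that every Study 2 outcome is compromised. Change in MT, SRC, rIHI and il_M1 SICE is not directly coupled and would be affected only through session-level error shared with the predictor. The fMRI predictor is not directly affected, and a 1-month SICE explaining a 6-month change would not share the error.

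A third reply is that this is an additional analysis. The Aim 2 hypothesis concerns M1 and corticospinal damage, and Study 3 derives the role of contralesional M1 from Study 1, not from SICE change. So the study's main conclusion does not rest on this model. The point still matters for any claim about state dependence drawn from it.

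Finally, a reader might assume that comparison with sham removes the problem on its own. It does not if the predictor is one session's own pre value.

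**Conclusion.** The concern holds in conditional form. The text puts cl_M1 SICE on both sides of the model, leaves the source of the predictor open, and includes neither a stimulation-condition factor nor any other safeguard. Depending on which recording is used, the false-positive rate for the cl_M1 SICE outcome is about 16–92% (same value), about 8–45% (averaged with one other recording) or 5% (independent recording). At r = 0.7 and n = 30 these are 58%, 20% and 5%.

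The figures rest on assumed reliability and patient numbers, equal variances, a two-sided test and one change score per patient. This is not a demonstrated error. It is more than a missing detail, because the text permits both a valid analysis and a badly biased one. It should be settled before the data are analysed.

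**What to change.** 1. State which recording supplies the Aim 1 SICE.
2. For the cl_M1 SICE outcome, do one of the following: take the predictor from a recording independent of both the active and the sham pre values; define it as the mean of the two pre values; or drop this outcome from the analysis.
3. Where sham pre/post TMS data exist, add stimulation condition to the model and test predictor × acquisition time × condition (1 Hz versus sham). Step 2 is still needed, because the contrast works only with a predictor that is independent of the two sessions or symmetric across them.

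Adding pre-rTMS SICE as a covariate beside a separate Aim 1 SICE is not a substitute. Both reflect the same true level, so the Aim 1 value still predicts the post value: under the same null model at r = 0.7 and n = 30 it is significant in about 63% of simulated trials.

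**Cost.** Where suitable recordings exist, this takes a sentence or two and one interaction with its lower-order terms, with no new visits. Power for the interaction is somewhat lower than for the uncontrolled association. If there is neither an independent recording nor a sham pre value, dropping the outcome is the remaining option.

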### 3. Objectives:

**A. Specific Aim #1: *Define key factors that determine the reorganization of contralesional M1 during post stroke recovery process by comparing M1 excitability of stroke patients to that of healthy subjects.*** Our working hypothesis is that the extent of M1 and/or corticospinal tract (CST) damage, as measured by the electromyographic response to TMS of lesioned M1, stroke lesion volume, increased fractional anisotropy (FA) asymmetry of the CST, and quality of wrist/finger extension movements, will determine the extent of contralesional M1 reorganization. In a subset of patients we will also use electroencephalography and TMS to determine the additional key factor of connectivity between the lesioned and the non- lesioned M1 in the post- stroke reorganizational process of contralesional M1.

**B. Specific Aim #2: *Determine the role of contralesional M1 in motor performance during the post stroke recovery process.*** Our working hypothesis is that, during recovery, contralesional M1 contributes to improved motor performance and recovery of the paretic hand in patients with larger M1 and/ or CST damage. Specifically, the extent of M1 and/or CST damage as measured by the electromyographic response to TMS of lesioned M1, lesion volume, increased FA asymmetry of the CST, and quality of wrist/finger extension movements(Nijland et al. 2010) will determine whether contralesional M1 plays a supportive or detrimental role in post-stroke recovery process.

At the completion of this project, we expect to have identified the extent to which

contralesional M1 reorganization determines motor performance during the different phases of post-stroke recovery and can be targeted by interventions depending on its “state” (role) in the recovery process. This latter knowledge would be expected to have a substantial positive impact on treatment for stroke patients as it will provide crucial evidence to develop evidence based TMS treatment protocols that are tailored to the state of therapeutic target. The clinically important question of whether decreasing contralesional M1 activity in patients post stroke is always helpful or at times is detrimental will be addressed.

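### Study #3 cuts each patient's rTMS effect to positive or negative, and the plan names no estimate or test of how damage relates to that effect, although Aim 2 predicts a direction

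*Combined protocol and SAP*

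**What the plan says.** **Hypothesis.** Section 3, Specific Aim #2, expects that "contralesional M1 contributes to improved motor performance and recovery of the paretic hand in patients with larger M1 and/ or CST damage". It names four measures of damage: the EMG response to TMS of lesioned M1, lesion volume, FA asymmetry of the corticospinal tract, and quality of wrist and finger extension. Their extent "will determine whether contralesional M1 plays a supportive or detrimental role in post-stroke recovery process".

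**Rule for the role.** Section 2 assigns the role by sign alone. Better performance after rTMS counts as supportive and worse performance as detrimental. No threshold is given.

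**Analysis.** In section 4.4, Study #3, "we will train (and test) a binary classifier to predict" patients' "responses (positive or negative) to rTMS (down regulation and sham) at 1 and 6 months post-stroke". On association, the text says: "The association between the set of predictors and the binary response will be established during an iterative cross-validation process". Performance is judged by sensitivity, specificity, PPV and NPV. Elastic Net, logistic and Bayes classifiers are compared, and the work is meant to "identify subsets of measures that have the greatest predictive power for forecasting the role of" contralesional M1.

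**The concern.** The hypothesis has a direction: more damage, more support from contralesional M1. The target of Study #3 keeps only the sign of each patient's effect. A patient just above zero and one far above it get the same label, and near zero that label is decided largely by measurement noise.

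The named outputs say how well the role can be forecast. They do not say which way damage points. The trial could therefore report that lesion volume predicts the role of contralesional M1 without having tested whether the relation runs as Aim 2 states. It would also have less chance of detecting the relation than the same data allow.

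**Working it through.** **1. Is the hypothesis tested anywhere else?** Each analysis in the plan was checked for a damage measure set against the rTMS effect on performance.

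- Section 4.3 (Aim 1 models): the factors are subject type, hemisphere and measure-specific factors, and the outcomes are TMS measures. The four damage measures do not appear as model terms.
- Section 4.4, Study #1: collects the effect of 1 Hz and sham rTMS on pointing performance, with no statistical analysis of its own.
- Section 4.4, Study #2: the mixed models name MT, SRC, SICE and IHI as outcomes. The added covariates are contralesional M1 excitability and activation, and the response is the change in TMS measures.
- Section 4.4, Study #3: the binary classifier.
- Section 6: refers back to these sections.

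Study #3 is the only link, and it names no coefficient, interval or test.

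**2. Can the named outputs show direction?** Suppose the damage-role relation were reversed. A classifier trained on those data would learn the reversed rule, with the same accuracy and the same selected predictors. Only the signs of fitted coefficients would differ, and the plan does not say they will be reported or tested.

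**3. Information lost by the cut.** The documents give no figure to reproduce. Assume a normal effect score, linear in one damage measure, with a share p of patients in the larger class. The efficiency of the cut outcome relative to the continuous one is φ(z_p)² / [p(1 − p)], where φ is the standard normal density and z_p the p-quantile.

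| Split | φ(z_p)² | p(1 − p) | Efficiency | Loss | Factor on N |
|---|---|---|---|---|---|
| 50:50 | 0.1592 | 0.25 | 0.637 (= 2/π) | 36% | 1.57 |
| 60:40 | 0.1493 | 0.24 | 0.622 | 38% | 1.61 |
| 70:30 | 0.1209 | 0.21 | 0.576 | 42% | 1.74 |
| 80:20 | 0.0784 | 0.16 | 0.490 | 51% | 2.04 |
| 90:10 | 0.0308 | 0.09 | 0.342 | 66% | 2.92 |

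**4. Sample size for 80% power.** Section 5 gives 30 healthy subjects and no number of stroke patients, so r and n are assumed. Section 4.3 gives alpha 0.05 and it is taken as two-sided. With n = [(1.960 + 0.842) / atanh(r)]² + 3 and r = 0.5:

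- Continuous: (2.802 / 0.549)² + 3, giving 30.
- Even cut: r shrinks to 0.5 × √0.637 = 0.399, giving 47.
- 80:20 cut: r shrinks to 0.5 × √0.490 = 0.35, giving 62.

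For r = 0.4 the three figures are 47, 75 and 98. For r = 0.3 they are 85, 135 and 176.

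**5. Simulated power.** One damage measure, bivariate normal, two-sided 0.05, 20,000 replicates:

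| n | r | Continuous | 50:50 cut | 80:20 cut |
|---|---|---|---|---|
| 20 | 0.5 | 64% | 44% | 33% |
| 30 | 0.3 | 37% | 25% | 20% |
| 30 | 0.4 | 61% | 42% | 33% |
| 30 | 0.5 | 83% | 62% | 49% |
| 40 | 0.5 | 92% | 75% | 62% |

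A separate simulation with 1,500 replicates gave 82% against 60% at n = 30 and r = 0.5, which agrees within simulation error.

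**The case against.** **The binary target is the documents' own.** Sections 2 and 3 frame the role as supportive or detrimental, and zero is the natural boundary between the two. This stands as a reason to keep the sign classification. It does not supply an estimate or test of the directional statement in section 3.

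**A reader might infer that Study #3 reports only accuracy and can never show direction.** The text does not support that. It also promises an association and predictor subsets, and it introduces the accuracy measures by way of example: "We will assess performance using standard measures of prediction accuracy such as sensitivity" and so on. Logistic and Elastic Net fits carry signed coefficients, so a reversed relation could be seen by anyone who looked. What is missing is a planned estimate, interval or test of that sign.

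**A reader might also take the 36% loss, or the power figures, as facts about this trial.** They are not. The loss depends on normality, linearity and an even split. The power figures compare simple tests on one predictor at one time point, whereas Study #3 plans multi-predictor, cross-validated classifiers at two time points. Nor can the patient sample be called small, because its size is not stated.

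**The performance variable is undefined.** Section 4.1.4 describes a pointing task with both movement time and hit-or-miss feedback, in the context of active IHI. Study #3 does not say which is used. Hits pooled over trials and compared with sham would still be graded, but as a bounded count to which the normal-theory figures do not carry over directly.

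**Conclusion.** The point holds in this form: the rTMS effect on performance is reduced to a sign, and no slope, direction, interval or test relating any damage measure to it is planned, although Aim 2 states a direction. That follows from the text and needs no assumption.

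The size is conditional. For a roughly normal score linear in damage, the loss is at least about 36%, rising to 42% at 70:30 and 51% at 80:20. The fall in power from about 82% to about 60% illustrates this for an assumed 30 patients and r = 0.5.

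One matter comes before any directional test. Section 2 says rTMS will transiently disrupt contralesional M1, yet it labels improvement after that disruption as supportive. These statements must be reconciled, or the sign of a slope cannot be read as evidence for or against Aim 2. This is a worthwhile improvement to the analysis of data already to be collected. It does not invalidate the design.

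**What to change.** 1. Reconcile the two statements in section 2, and write down which sign of the rTMS effect means supportive.
2. In section 4.4, name one graded, sham-corrected change in paretic-hand pointing performance, for example in movement time. State how the four complexity levels are combined, and keep the measure continuous.
3. As the Aim 2 test, fit a mixed model in patients only, with stimulation (1 Hz or sham), damage, their interaction and time post-stroke (1 and 6 months). Use one prespecified damage measure or composite, or all four with a multiplicity correction. Report the interaction as a slope, with its direction and 95% CI.
4. Fit the Elastic Net to the continuous outcome. Derive the sign from its prediction, and report sensitivity, specificity, PPV and NPV as secondary results.

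Cost: SAP wording, a few extra model fits, and one damage measure to choose in advance. No new data or visits are needed. Testing all four measures has a price. At alpha 0.05 / 4 = 0.0125, with the same assumed 30 patients and r = 0.5, power for each measure falls from 83% to about 65% with the continuous outcome, and from 62% to just under 40% with an even cut. The relative gain survives, but a single primary measure or composite is the better choice.
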